##### 1.4.2. Maintenance Phase (Day 1 up to Week 100)

There are two ways in which study participants may transition to the LA regimen, either directly from oral SOC or from Q4W dosing from ATLAS.

The Table and Figure below describe the CAB LA + RPV LA dosing regimens in ATLAS-2M based on the mode of transition.

[figure not shown]
#### CAB LA + RPV LA Dosing Regimens in ATLAS-2M

Participants Transitioning from Oral Standard of Care (SOC)		
Regimen	CAB LA	RPV LA
Q4W	CAB LA: Week 4b: 600 mg (Loading Dose) Week 8 & Q4W thereafter: 400 mg	RPV LA: Week 4b: 900 mg (Loading Dose) Week 8 & Q4W thereafter: 600 mg
Q8W	CAB LA: Week 4b, Week 8, & Q8W thereafter: 600 mg	RPV LA: Week 4b, Week 8, & Q8W thereafter: 900 mg

Participants Transitioning from ATLAS Q4W		
Regimen	CAB LA	RPV LA
Q4W	CAB LA: Day 1 & Q4W thereafter: 400 mg	RPV LA: Day 1 & Q4W thereafter: 600 mg
Q8W	CAB LA: Day 1 & Q8W thereafter: 600 mg	RPV LA: Day 1 & Q8W thereafter: 900 mg

All participants entering ATLAS-2M from an oral SOC regimen will receive a 4-week oral lead-in of CAB+RPV prior to receiving IM injections, except for ATLAS subjects transitioning from Q4W to Q8W injections. These participants previously established safety and tolerability of CAB + RPV within the ATLAS study.

**ATLAS-2M Treatment Schematic**

**1.4.2.1. Patients randomized to LA dosing from current ART SOC therapy:**

All participants randomized from current ART SOC therapy (including those transitioning from SOC in ATLAS and new study participants) will begin oral therapy with CAB 30 mg + RPV 25 mg once daily at Day 1 for 4 weeks to determine individual safety and tolerability prior to administration of CAB LA + RPV LA. The oral lead-in period is part of the Maintenance Phase and will therefore be included within the Week 48, 96, and 152 planned analyses.

The final dosing of current daily oral ART regimen should occur the day prior to randomization to avoid overlap of treatment regimens however, if the participant takes

current ART prior to coming into the clinic, randomization and initiation of oral CAB and RPV should continue as planned for Day 1. At the Week 4a visit, safety assessments (including e.g., clinical chemistries) will be performed as per the Time and Events Table to determine individual safety and tolerability prior to the initial administration of CAB LA + RPV LA. Dosing of CAB LA + RPV LA Q4W or Q8W will initiate at the Week 4b visit once safety labs from Week 4a are available and have been reviewed.

Subjects receiving oral SOC treatment and randomized to Q4W injections will receive loading doses of CAB LA 600 mg + RPV LA 900 mg on **Week 4b** followed by maintenance injections of CAB LA 400 mg + RPV LA 600 mg every 4 weeks thereafter.

Subjects receiving oral SOC treatment and randomized to Q8W injections will receive doses of CAB LA 600 mg + RPV LA 900 mg on **Week 4b and Week 8** followed by identical maintenance dose injections every 8 weeks thereafter.

All injections should be planned as single injections per drug.

**1.4.2.1.1. IM injections every 4 weeks (Q4W from SOC):**

Week 4b visit only - CAB LA 600 mg + RPV LA 900 mg, each given as 1 X 3 mL IM injection

Week 8 visit and Q4W thereafter - CAB LA 400 mg IM + RPV LA 600 mg IM every 4 weeks for 100 weeks, each given as 1 X 2 mL IM injection

At Week 4b, participants will return to the clinic, take the last oral dose (CAB 30 mg + RPV 25 mg), and receive the first CAB LA (600 mg) + RPV LA (900 mg) injections (within 2 hours of the final oral dose of CAB + RPV). The first injection visit with IM CAB LA + RPV LA at Week 4b can be performed once central lab results are available and safety parameters are reviewed from the Week 4a visit.

The second and third IM injections with CAB LA 400 mg and RPV LA 600 mg will be performed at Week 8 and Week 12. There will be a -7-day dosing window for the second and third IM injections such that the second injection occurs within the window of Week 7 and Week 8 but no later than Week 8 and the third injection occurs within the window of Week 11 and Week 12 but no later than Week 12. Subsequent injections with CAB LA 400 mg and RPV LA 600 mg will occur every 4 weeks ( $\pm 7$  days) thereafter. In addition, starting after the Week 16 injection, the interval between injection visits will be limited to a maximum of 5 weeks. The Medical Monitor must be contacted to discuss individual participant case management if the length of time between injections exceeds or is projected to exceed 5 weeks.

**1.4.2.1.2. IM injections every 8 weeks (Q8W from SOC):**

Week 4b visit – CAB LA 600 mg + RPV LA 900 mg IM, each given as 1 X 3 mL IM injection

Week 8 visit- CAB LA 600 mg + RPV LA 900 mg IM, each given as 1 X 3 mL IM injection

Week 16 visit and Q8W thereafter - CAB LA 600 mg + RPV LA 900 mg IM, every 8 weeks for 100 weeks, each given as 1 X 3 mL IM injection

At the Week 4b visit, subjects will return to the clinic, take their last oral dose (CAB 30 mg + RPV 25 mg), and receive the first CAB LA (600 mg) + RPV LA (900 mg) injections (within 2 hours of the final oral dose of CAB + RPV). The first injection visit with IM CAB LA + RPV LA at Week 4b can be performed once central lab results are available and safety parameters are reviewed from the Week 4a visit.

The second loading injection will be administered at Week 8 (CAB LA 600 mg + RPV LA 900 mg), with subsequent injections (CAB LA 600 mg + RPV LA 900 mg) occurring every 8 weeks thereafter. There will be a -7-day dosing window for the second and third IM injections such that the second injection occurs within the window of Week 7 and Week 8 but no later than Week 8 and third injection occurs within the window of Week 15 and Week 16 but no later than Week 16. Subsequent injections with CAB LA 600 mg and RPV LA 900 mg will occur every 8 weeks ( $\pm 7$  days). Starting after the Week 16 injection, the interval between injection visits will be limited to a maximum of 9 weeks. If the length of time between injections exceeds, or is projected to exceed 9 weeks, the Medical Monitor must be contacted to discuss individual participant case management.

#### **1.4.2.2. Participants transitioning from ATLAS and currently receiving CAB LA + RPV LA Q4W**

Subjects receiving Q4W injections within ATLAS and randomized to receive Q4W injections in ATLAS-2M, will continue receiving maintenance injections Q4W as scheduled and will not require a loading dose on Day 1.

Subjects receiving Q4W injections within ATLAS and randomized to receive Q8W injections in ATLAS-2M will receive doses of CAB LA 600 mg + RPV LA 900 mg on Day 1 one month after their last Q4W maintenance dose in order to align with day of study randomization. Subjects will not require an intermediate dose at Week 4 and will receive their next Q8W maintenance injections at Week 8 and Q8W thereafter.

Participants transitioning from the ATLAS study and on CAB LA + RPV LA Q4W treatment will be randomized at Day 1 to either continue Q4W administration or transition to Q8W administration of CAB LA + RPV LA. The first injection visit for the ATLAS-2M study can be performed once the final central lab results from the ATLAS study are available and safety parameters have been reviewed. Screening labs determining eligibility for ATLAS-2M can be collected at Week 48 (at minimum) for participants originally randomized to the Q4W arm within ATLAS. Screening labs for participants who recently transitioned from SOC to Q4W injections within the ATLAS Extension Phase may be obtained at ATLAS Week 56b (after completion of the CAB + RPV Oral lead-in period) or at a subsequent ATLAS visit after receiving one set or a short course of Q4W injections. The transition from the final ATLAS to ATLAS-2M Day 1 dosing must occur 4 weeks ( $\pm 7$  days) from the final injections received in ATLAS.

Dosing for participants transitioning from CAB LA + RPV LA Q4W in ATLAS is as follows:

**1.4.2.2.1. IM injections every 4 weeks (Q4W from ATLAS Q4W):**

Starting at Day 1, all injections will continue with the maintenance dose of CAB LA 400 mg and RPV LA 600 mg administered every 4 weeks ( $\pm 7$  days). In addition, the time between injection visits will be limited to a maximum of 5 weeks. The Medical Monitor must be contacted if the length of time between injections exceeds or is projected to exceed 5 weeks.

**1.4.2.2.2. IM injections every 8 weeks (Q8W from ATLAS Q4W):**

Participants transitioning from ATLAS and randomized to receive CAB LA + RPV LA Q8W injections will initiate Q8W dosing at the Day 1 visit as follows:

Day 1- CAB LA 600 mg + RPV LA 900 mg IM, each given as 1 X 3 mL IM injection

Week 8 and Q8W thereafter- CAB LA 600 mg + RPV LA 900 mg IM, each given as 1 X 3 mL IM injection

The second injection will be administered at Week 8 (CAB LA 600 mg + RPV LA 900 mg, with subsequent injections (CAB LA 600 mg + RPV LA 900 mg) occurring every 8 weeks thereafter. There will be a -7-day dosing window for the second and third IM injections such that the second injection occurs within the window of Week 7 and Week 8 but no later than Week 8 and third injection occurs within the window of Week 15 and Week 16 but no later than Week 16. Subsequent injections with CAB LA 600 mg and RPV LA 900 mg will occur every 8 weeks ( $\pm 7$  days). Starting after the Week 16 injection, the interval between injection visits will be limited to a maximum of 9 weeks. If the length of time between injections exceeds, or is projected to exceed 9 weeks, the Medical Monitor must be contacted to discuss individual participant case management.

The primary study analysis will consist of data collected through the Week 48 visit. A single repeat of HIV-1 RNA for any participant with a HIV-1 RNA  $\geq 50$  c/mL at Week 48, Week 96, or Week 152 must be performed. The retest should be scheduled as soon as possible (but no later than 4 weeks from the Week 48, Week 96, or Week 152 visits, respectively) and will inform the Week 48, Week 96, or Week 152 virological endpoint, respectively.

**1.4.3. Extension Phase**

Participants who successfully complete 96 Weeks of CAB LA + RPV LA treatment in the Maintenance Phase will continue to have access to their randomized treatment Q4W or Q8W CAB LA + RPV LA in the Extension Phase through Week 152 and until study treatment is either locally approved and commercially available within the local sector (including through local public/government health sectors), the participant no longer derives clinical benefit, the participant meets a protocol-defined reason for discontinuation or until development of either CAB LA + RPV LA Q4W and/or Q8W is terminated. For participants randomized to Q4W arm, dosing visits will continue to occur every 4 weeks with CAB LA 400mg and RPV LA 600 mg. For participants randomized to the Q8W arm, dosing visits will continue to occur every 8 weeks with

CAB LA 600 mg and RPV LA 900 mg. Safety and efficacy assessments will be conducted as per the Time and Events Schedule.

Participants choosing to not enter the Extension phase can complete their study participation at the Week 100 visit and enter into the LTFU Phase as required.

Participants who choose to continue on to the Extension Phase will need to be assessed for eligibility and will continue on their current CAB LA + RPV LA regimen while eligibility is being confirmed. A single repeat of HIV-1 RNA for any participant with a HIV-1 RNA  $\geq 50$  c/mL and  $< 400$  c/mL at Week 96 or Week 152 must be performed. The retest should be scheduled as soon as possible (but no later than 4 weeks from the Week 96 or Week 152 visit). Participants with HIV-1 RNA  $< 50$  c/mL upon retest are eligible to enter the Extension Phase. Participants with HIV-1 RNA  $\geq 400$  c/mL at Week 96 are not eligible to enter the Extension Phase, will not be allowed a repeat to determine eligibility, and will therefore be withdrawn from the study treatment. Eligibility to enter the Extension Phase for any participants with a retest HIV-1 RNA  $> 50$  c/mL and  $< 400$  c/mL will require approval by the study Medical Monitor.

Participants not eligible to enter the Extension Phase or choosing not to participate in the Extension Phase will end their study treatment and enter the LTFU Phase. Sites may be reimbursed for up to a one-month supply of antiretroviral medication to facilitate transition to non-study ART for participants that do not qualify for the Extension Phase.

#### 1.4.4. Long-Term Follow-Up Phase

- Any participant who receives at least one dose of CAB LA and/or RPV LA and discontinues the CAB LA + RPV LA regimen for any reason before CAB LA + RPV LA marketed product is locally available must enter the LTFU Phase. Participants must remain on suppressive HAART for at least 52 weeks after the last dose of CAB LA and/or RPV LA in order to prevent selective pressure on HIV and the potential for selection of resistant mutants. **Investigators must discuss the choice of the follow-up HAART regimen with the Medical Monitor prior to initiating the new regimen with the participant. HAART therapy should be initiated within 4 weeks (+7 days) after the last Q4W injection, or within 8 weeks (+7 days) after the last Q8W injection.** The LTFU Phase will begin the day of the last CAB LA and/or RPV LA dose and continue for 52 weeks.. Upon discontinuation from the Maintenance or Extension Phase, these participants will complete Withdrawal assessments (see Section 5.5) and will then enter into the LTFU Phase as per the Time and Events Schedule (Section 7.1).
- Where the CAB LA + RPV LA marketed product is locally available, only participants that discontinue the CAB LA + RPV LA regimen for **safety-related reasons** included in Section 5.5, must enter the LTFU Phase. Participants must remain on suppressive HAART for at least 52 weeks after the last dose of CAB LA and/or RPV LA in order to prevent selective pressure on HIV and the potential for selection of resistant mutants. **Investigators must discuss the choice of the follow-up HAART regimen with the Medical Monitor prior to**

**initiating the new regimen with the participant. HAART therapy should be initiated within 4 weeks ( $\pm$  7 days) after the last Q4W injection, or within 8 weeks ( $\pm$  7 days) after the last Q8W injection.** The LTFU Phase will begin the day of the last CAB LA and/or RPV LA dose and continue for 52 weeks. These participants will complete Withdrawal assessments prior to entering into the LTFU Phase as per the Time and Events Schedule. In addition, for participants who withdraw during the LTFU, the final visit will be considered the study withdrawal visit.

- NOTE: Participants transitioning to CAB+RPV LA marketed product or alternative HAART (except due to safety-related reasons) do not need to enter the LTFU Phase.

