**4.2.2.1.1. IM injections every 4 weeks (Q4W from SOC):**

Week 4b visit only - CAB LA 600 mg + RPV LA 900 mg, each given as 1 X 3 mL IM injection

Week 8 visit and Q4W thereafter - CAB LA 400 mg IM + RPV LA 600 mg IM every 4 weeks for 100 weeks, each given as 1 X 2 mL IM injection

At Week 4b, participants will return to the clinic, take the last oral dose (CAB 30 mg + RPV 25 mg), and receive the first CAB LA (600 mg) + RPV LA (900 mg) injections (within 2 hours of the final oral dose of CAB + RPV). The first injections with IM CAB LA + RPV LA at Week 4b can be performed once central lab results are available and safety parameters are reviewed from the Week 4a visit.

The second and third IM injections with CAB LA 400 mg and RPV LA 600 mg will be performed at Week 8 and Week 12. There will be a -7-day dosing window for the second and third IM injections such that the second injection occurs within the window of Week 7 and Week 8 but no later than Week 8 and the third injection occurs within the window of Week 11 and Week 12 but no later than Week 12. Subsequent injections with CAB LA 400 mg and RPV LA 600 mg will occur every 4 weeks ( $\pm 7$  days) thereafter. In addition, starting after the Week 16 injection, the interval between injection visits will be limited to a maximum of 5 weeks. The Medical Monitor must be contacted to discuss individual participant case management if the length of time between injections exceeds or is projected to exceed 5 weeks.

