**4.2.2.1.2. IM injections every 8 weeks (Q8W from SOC):**

Week 4b visit – CAB LA 600 mg + RPV LA 900 mg IM, each given as 1 X 3 mL IM injection

Week 8 visit- CAB LA 600 mg + RPV LA 900 mg IM, each given as 1 X 3 mL IM injection

Week 16 visit and Q8W thereafter - CAB LA 600 mg + RPV LA 900 mg IM, every 8 weeks for 100 weeks, each given as 1 X 3 mL IM injection

At the Week 4b visit, subjects will return to the clinic, take their last oral dose (CAB 30 mg + RPV 25 mg), and receive the first CAB LA (600 mg) + RPV LA (900 mg) injections (within 2 hours of the final oral dose of CAB + RPV). The first injections with IM CAB LA + RPV LA at Week 4b can be performed once central lab results are available and safety parameters are reviewed from the Week 4a visit.

The second loading injection will be administered at Week 8 (CAB LA 600 mg + RPV LA 900 mg, with subsequent injections (CAB LA 600 mg + RPV LA 900 mg) occurring every 8 weeks thereafter. There will be a -7-day dosing window for the second and third IM injections such that the second injection occurs within the window of Week 7 and Week 8 but no later than Week 8 and third injection occurs within the window of Week 15 and Week 16 but no later than Week 16. Subsequent injections with CAB LA 600 mg and RPV LA 900 mg will occur every 8 weeks ( $\pm 7$  days). Starting after the Week 16

injection, the interval between injection visits will be limited to a maximum of 9 weeks. If the length of time between injections exceeds, or is projected to exceed 9 weeks, the Medical Monitor must be contacted to discuss individual participant case management.

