#### 4.2.4. LTFU Phase – IM Regimen Only

- Any participant who receives at least one dose of CAB LA and/or RPV LA and discontinues the CAB LA + RPV LA regimen for any reason before CAB LA + RPV LA marketed product is locally available must enter the LTFU Phase. Participants must remain on suppressive HAART for at least 52 weeks after the last dose of CAB LA and/or RPV LA in order to prevent selective pressure on HIV and the potential for selection of resistant mutants. **Investigators must discuss the choice of the follow-up HAART regimen with the Medical Monitor prior to initiating the new regimen with the participant. HAART therapy should be initiated within 4 weeks ( $\pm$  7 days) after the last Q4W injection or within 8 weeks ( $\pm$  7 days) after the last Q8W injection.** The LTFU will begin the day of the last CAB LA and/or RPV LA dose and continue for 52 weeks. These participants will complete Withdrawal assessments and will then enter into the LTFU Phase as per the Time and Events Schedule. In addition, for participants who withdraw during the LTFU Phase, the final visit will be considered the study withdrawal visit.
- Where the CAB LA + RPV LA marketed product is locally available, only participants that discontinue the CAB LA + RPV LA regimen for **safety-related reasons** included in Section 5.5 must enter the LTFU Phase. Participants must remain on suppressive HAART for at least 52 weeks after the last dose of CAB LA and/or RPV LA in order to prevent selective pressure on HIV and the potential for selection of resistant mutants. **Investigators must discuss the choice of the follow-up HAART regimen with the Medical Monitor prior to initiating the new regimen with the participant. HAART therapy should be initiated within 4 weeks ( $\pm$  7 days) after the last Q4W injection or within 8 weeks ( $\pm$  7 days) after the last Q8W injection.** The LTFU Phase will begin the day of the last CAB LA and/or RPV LA dose and continue for 52 weeks. These participants will complete Withdrawal assessments and will then enter into the LTFU Phase as per the Time and Events Schedule. In addition, for participants who withdraw during the LTFU Phase, the final visit will be considered the study withdrawal visit.

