**4.5.2.1. CAB LA Q8W**

The CAB LA 600mg Q8W regimen is predicted to achieve concentrations above 1.35 µg/mL, the geometric mean Cτ following oral CAB 10 mg once daily which was shown to be efficacious in the LATTE study. The lower bound of the 90% prediction interval is approximately 0.166 µg/mL, indicating that 95% of subjects on this regimen should remain above the PA-IC90 throughout dosing (Figure 4). The CAB LA Q8W regimen consists of identical 600 mg doses administered at Day 1, Week 4, and Q8W thereafter.

**Figure 4 Simulated\* Median (90% Prediction Interval [PI]) CAB Plasma Concentrations versus Time for the Optimized CAB LA Q8W Regimen (600 mg IM Day 1, Week 4, Q8W Thereafter)^**

\*Note: current simulations based on interim plasma concentration dataset

[figure not shown]
[figure not shown]
^Study Time and Events include a 4-week oral lead in for subjects transitioning to Q8W from oral SOC. Therefore, Day 1 (time zero) = date of first injections in 207966

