**Figure 7 Predicted CAB Profiles for CAB LA Q8W after Transition from Oral**

A one-week delay in CAB LA dosing for the Q8W regimen at steady state is predicted to result in ~92% rather than 95% of subjects achieving trough concentrations above the PA-IC90, which is considered acceptable.

[figure not shown]

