At steady-state, a one-week delay in dosing for the Q8W regimen is predicted to result in a median steady-state  $C_{\tau}$  that is approximately 11% lower (48 ng/mL) than for dosing that is administered on schedule, with >99% of subjects still remaining above the RPV PA-IC90. This supports allowance of some flexibility in the dosing regimen in ATLAS-2M, similar to what is currently practiced in the LATTE-2 study.

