#### **6.9.1.2. IM injections every 8 weeks (Q8W):**

Week 4b – CAB LA 600 mg + RPV LA 900 mg IM, each given as 1 X 3 mL IM injection

Week 8 - CAB LA 600 mg + RPV LA 900 mg IM, each given as 1 X 3 mL IM injection

Week 16 and Q8W thereafter - CAB LA 600 mg + RPV LA 900 mg IM, every 8 weeks for 100 weeks, each given as 1 X 3 mL IM injection

At Week 4b, subjects will return to the clinic, take the last dose of their oral (CAB 30 mg + RPV 25 mg), and receive the first CAB LA (600 mg) + RPV LA (900 mg) injections (within 2 hours of the final oral dose of CAB + RPV). The first injection visit with IM CAB LA + RPV LA at Week 4b can be performed once central lab results are available and safety parameters are reviewed from the Week 4a visit.

The second loading injection will be administered at Week 8 (CAB LA 600 mg + RPV LA 900 mg, with subsequent injections (CAB LA 600 mg + RPV LA 900 mg) occurring every 8 weeks thereafter. The dosing window for the second injection allows administration between Week 7 and Week 8, but preferably not later than Week 8. After Week 16, a dosing window ( $\pm 7$  days) for injections is allowed, but not preferred. Starting at the Week 16 injection, the interval between injection visits should be limited to a maximum of 9 weeks. If the length of time between injections exceeds, or is projected to exceed 9 weeks, the Medical Monitor must be contacted to discuss individual subject case management

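### After a lone Week 4b loading injection, HAART may start as late as 9 weeks on Q8W but 5 weeks on Q4W, although both arms received the same dose

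*Protocol*

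**What the plan says.** - **HAART limit.** Section 1.4.4: "HAART therapy should be initiated within 4 weeks (+7 days) after the last Q4W injection, or within 8 weeks (+7 days") for Q8W. Section 4.2.4 writes ± 7 days, so the latest dates are the same. The resistance rows of the Section 2.3.1 risk tables give 4 and 8 weeks without the extra 7 days.
- **Who is covered.** Section 4.2.4: "Any participant who receives at least one dose of CAB LA and/or RPV LA and discontinues the CAB LA + RPV LA regimen". While marketed product is not yet locally available, this holds whatever the reason for stopping. Once it is available, the same limits apply to those who stop for safety-related reasons. Neither bullet makes an exception for someone who has had only the first injection.
- **First injection.** Q4W entrants from standard of care (Section 4.2.2.1.1): "Week 4b visit only - CAB LA 600 mg + RPV LA 900 mg, each given as 1 X 3 mL IM injection". Section 4.2.2.1.2 gives Q8W entrants the same two doses at Week 4b.
- **Second injection on Q8W.** Section 4.5.2.1: "The CAB LA Q8W regimen consists of identical 600 mg doses administered at Day 1, Week 4, and Q8W thereafter", where Day 1 means the first injection. Section 4.2.2.1.2 requires that "the second injection occurs within the window of Week 7 and Week 8 but no later than Week 8". Section 6.9.1.2 is softer: "The dosing window for the second injection allows administration between Week 7 and Week 8, but preferably not later than Week 8".
- **Support for a 9-week gap.** CAB (Section 4.5.2.1.1, after Figure 7): "A one-week delay in CAB LA dosing for the Q8W regimen at steady state is predicted to result in ~92% rather than 95"% above the PA-IC90. RPV (Section 4.5.3.1.1): "At steady-state, a one-week delay in dosing for the Q8W regimen is predicted to result in a median steady-state" trough about 11% lower, at 48 ng/mL, with more than 99% above the PA-IC90.
- **Withdrawal visit between planned visits (Section 5.5).** It is due within 4 weeks of the last Q4W injection or 8 weeks of the last Q8W injection, and its assessments must come before the next ART regimen.

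**The concern.** Drug levels after one injection depend on the dose given, not on the regimen the participant would have gone on to receive. Up to the planned second injection, entrants from standard of care in the two arms have had identical treatment. A deadline that differs by 4 weeks between them therefore has no pharmacological basis in the text.

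Elsewhere the protocol is stricter when few injections have been given. In Sections 1.4.2.1.2 and 4.2.2.1.2 the second and third Q8W injections may be early but not late, and the 9-week maximum interval applies only after Week 16. The intermediate dose is waived only for participants coming from Q4W, because their CAB levels are already above the Q8W targets (Section 4.5.2.1.1). The HAART rule gives the longest allowance to people who have had a single dose.

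Section 2.3.1 presents prompt HAART as the safeguard against emergent resistance after stopping. What is at stake is the resistance risk of an individual who stops early, not the trial's comparison.

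**Working it through.** **1. Reproducing the protocol's own figure.** The fall in the RPV steady-state trough after a one-week delay, from 54 ng/mL (Section 4.5.3.1) to 48 ng/mL (Section 4.5.3.1.1), is 1 − 48/54 = 11.1%, against a stated figure of about 11%. It reproduces.

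**2. Latest dates after the same Week 4b injection.**

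| | Q4W | Q8W | Difference |
|---|---|---|---|
| HAART, Sections 1.4.4 and 4.2.4 | 4×7 + 7 = 35 days | 8×7 + 7 = 63 days | 28 days |
| HAART, Section 2.3.1 | 28 days | 56 days | 28 days |
| Between-visit withdrawal visit, Section 5.5 | 28 days | 56 days | 28 days |
| Next injection if treatment continues | about 28 days | about 28 days | 0 |

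The Q8W HAART limit falls 63 − 28 = 35 days after the missed second injection (28 days under Section 2.3.1). The Q4W limit falls 35 − 28 = 7 days after it.

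**3. RPV 8 weeks after one 900 mg dose.** LATTE-2 left this gap (Section 4.5.2) and observed 30 ng/mL (Section 4.5.3.1).
- Ratio to the PA-IC90 of 12 ng/mL: 30/12 = 2.5.
- Shortfall from the predicted steady-state median: (54 − 30)/54 = 44%.
- Share below the PA-IC90, assuming log-normal levels with median 30: Φ(−ln 2.5/σ), where σ = √ln(1 + CV²). The two first-dose, week-4 CVs in Table 6 are 34% and 64% (healthy subjects, 1200 mg, n=10 and n=9).
  - CV 34%: σ = 0.331, giving 0.3%.
  - CV 64%: σ = 0.586, giving 5.9%.
- Ceiling from the statement that more than 92% are above 12 ng/mL at Week 4 with median 40: σ ≤ ln(40/12)/z(0.92) = 0.857, giving at most 14%. This is a bound, not an estimate.

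**4. RPV at 9 weeks.** No value is given. Assuming the steady-state weekly fall also applies here, the median is 30 × 48/54 = 26.7 ng/mL, or 26.7/12 = 2.2 times the PA-IC90. The same log-normal calculation with ln(26.7/12) puts 0.8% (CV 34%) to about 9% (CV 64%) below it.

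**5. CAB.** The document shown gives no level 8 or 9 weeks after one 600 mg dose. LATTE-2 gave 800 mg and then 600 mg at Week 4 (Section 4.5.2), so it did not test this gap. Extrapolating from Table 5 would need dose proportionality from an 800 mg dose in ten healthy subjects and a borrowed rate of decline. I put no figure on it.

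**The case against.** The best defence is that the limit is only a backstop. The next scheduled contact on Q8W is the Week 8 visit, and stopping there triggers withdrawal assessments at that visit (Section 5.5). A missed visit obliges the site to make contact and reschedule. The Medical Monitor must be involved in missed doses, out-of-window dosing and any interruption (Sections 4.2.5 and 6.9.1). Section 6.9.1 also tells investigators to ensure alternative ART as levels decline. This stands as mitigation and makes a 9-week gap unlikely. None of these rules sets a shorter date, though, so a site can follow the protocol and still reach day 63. Only the first part of the protocol is shown, without the appendices or the procedures manual, so a shorter limit there cannot be excluded.

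A reader might infer that participants who use the full Q8W limit would fall to ineffective levels. The documents do not show this. RPV was 2.5 times the PA-IC90 at 8 weeks. The modelled 0.3% to 5.9% below it lies within what the protocol already accepts on schedule, since more than 92% above at Week 4 allows up to 8% below. The 5.9% rests on nine healthy subjects at a higher dose. The Q8W trough CVs in HIV-infected participants, 35% to 41% in Table 6 (later intervals), give about 0.3% to 1.0%. For CAB there is no visible level in either direction.

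A reader might also infer that every limit of 8 weeks (+7 days) before steady state is wrong. That goes too far. Participants who stop after the Week 8 injection, or who came from a short course of Q4W, may not be at steady state either, but they have had more than one dose. The identical-dose comparison between arms does not apply to them.

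**Conclusion.** The inconsistency is real and low in severity. After one identical injection, the protocol allows HAART to start 28 days later on Q8W than on Q4W, although the next dose was due at the same time and the stated support for a 9-week gap is limited to steady state. It concerns only entrants from standard of care who stop after Week 4b. That group is small, and the protocol does not give its size.

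Harm is not demonstrated. RPV at 8 weeks is partly reassuring, RPV at 9 weeks rests on an assumed decline, and CAB is unknown. A reader might suspect a bias between the arms, but no trial endpoint is affected. The date on which HAART starts after stopping does not enter the Week 48 primary endpoint, and the resistance endpoint is restricted to confirmed virologic failure, whose definition does not apply in long-term follow-up (Section 5.5.5).

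The conclusion rests on the text shown and on reading the limit by randomized arm, as it is written. It is an optional, cheap improvement.

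**What to change.** - **Sections 1.4.4 and 4.2.4:** add that after a Week 4b loading injection with no later injection, HAART should start within 4 weeks (+7 days) in either arm.
- **Section 2.3.1, both resistance rows:** align with that sentence.
- **Section 5.5:** after a lone Week 4b injection, set the between-visit withdrawal visit within 4 weeks (+7 days) in either arm and before HAART starts. The extra 7 days matter here. Without them, the deadline could already have passed for someone who decides to stop just after a missed Week 8 visit.
- Leave the other limits as they are, without claiming that they rest on steady-state data.

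The cost is wording in five places, with no new visits, samples or data. The downside is that a Q8W participant who stops after Week 4b must start HAART up to 4 weeks earlier than now (63 − 35 = 28 days). The new limit is the one Q4W participants already follow after the same dose.
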